#### **4.3. Protocol Deviations**

A summary of important protocol deviations will be provided by the Clinical Operations group for subjects in the Safety Analysis Set.

## 5. BASELINE DATA

### 5.1. Demographics

Subject demographic variables (ie, age, sex, race, and ethnicity) will be summarized by genotype and using descriptive statistics (n, mean, SD, median, Q1, Q3, minimum, and maximum) for age and BMI ( $\text{kg}/\text{m}^2$ ), and using the numbers and percentages of subjects for age categories ( $< 65$  years,  $\geq 65$  years), BMI categories ( $< 30 \text{ kg}/\text{m}^2$ ,  $\geq 30 \text{ kg}/\text{m}^2$ ), sex, race, and ethnicity. Age is calculated in years at the date of initial study drug administration. If a subject did not receive study drug after enrollment, the subject's age will be calculated from the date that the subject signed the informed consent form. The summary of demographic data will be provided for the Safety Analysis Set by HCV genotype and treatment group.

A by-subject demographic listing, which includes first dose date, will be provided by subject ID number in ascending order.

### 5.2. Other Baseline Characteristics

Other baseline characteristics include:

- HCV genotype and subtypes
- IL28B (CC, Non-CC (including CT, and TT))
- baseline HCV RNA as a continuous variable and as categories ( $< 800,000 \text{ IU}/\text{mL}$ ,  $\geq 800,000 \text{ IU}/\text{mL}$ )
- baseline ALT as a continuous variable and for categories ( $\leq 1.5 \times \text{ULN}$ ,  $> 1.5 \times \text{ULN}$ )
- prior HCV treatment experience (treatment naïve, treatment experienced)
- cirrhosis (presence, absence, missing)
- renal transplant (yes, no)
- prior HCV treatment for treatment experienced subjects [DAA Naive (Peg-IFN + RBV, Other)]
- prior HCV treatment response (non-responder, relapse/breakthrough, early treatment discontinuation, and unknown) for treatment experienced subjects
- type of current dialysis (Hemodialysis, Peritoneal Dialysis)

These baseline characteristics will be summarized by genotype using descriptive statistics (n, mean, SD, median, Q1, Q3, minimum, and maximum) for continuous variables and using the numbers and percentages of subjects for categorical variables. The summary of baseline characteristics will be provided for the Safety Analysis Set.

A by-subject listing of other baseline characteristics will be provided by subject ID number in ascending order.

A separate by-subject data listing for cirrhosis determination will be provided for all subjects at screening.

A separate by-subject data listing for prior HCV treatment and response will be provided for all treatment experienced subjects. The listing will display the prior HCV regimen(s) and treatment(s) including the treatment duration, and the prior HCV treatment response.

### **5.3. Medical History**

Medical history collected at screening will be coded using the current Medical Dictionary for Regulatory Activities (MedDRA). Medical history will be summarized by system organ class (SOC), preferred term (PT), treatment group, and overall. Subjects who report 2 or more medical history items that are coded to the same SOC and/or PT will be counted only once by the unique coded term in the summary. The summary will be provided for the Safety Analysis Set. No inferential statistics will be generated.

A by-subject listing of disease-specific medical history will be provided by subject ID number (in ascending order) and medical history of abnormalities (in chronological order).

A by-subject listing of renal transplant will be provided by subject ID number.

## 6. EFFICACY ANALYSES

### 6.1. Primary Efficacy Endpoint

#### 6.1.1. Definition of the Primary Efficacy Endpoint

The primary efficacy endpoint is SVR12 defined as HCV RNA < LLOQ 12 weeks after discontinuation of study drug in the FAS. The COBAS® AmpliPrep/COBAS® TaqMan® HCV Quantitative Test, v2.0 will be used to measure HCV RNA. The LLOQ for this assay is 15 IU/mL.

#### 6.1.2. Primary Analysis of the Primary Efficacy Endpoint

The SVR12 rate in each of genotype will be calculated along with 2-sided 95% exact CI based on Clopper-Pearson method {[Clopper 1934](#)}.

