Pharmacokinetics: The PK of LDV and SOF (and metabolites) may be assessed.

Statistical Methods: The primary efficacy endpoint for the study is SVR12 in all enrolled and treated subjects.

In the primary efficacy analysis, the point estimate and the 2-sided 95% exact confidence interval of SVR12 rate will be provided for each treatment group and overall.

With a sample size of 100 subjects, a 2-sided 95% exact confidence interval will extend at the most 20% in length.

Secondary efficacy endpoints include SVR4, SVR24, and the proportion of subjects with virologic failure. Steady state PK plasma parameters will be listed by subject and summarized by treatment group and overall using descriptive statistics for each analyte (SOF [and its metabolites] and LDV, as appropriate).

This study will be conducted in accordance with the guidelines of Good Clinical Practice (GCP) including archiving of essential documents.

GLOSSARY OF ABBREVIATIONS AND DEFINITION OF TERMS

° C	degrees Celsius
° F	degrees Fahrenheit
Ab	antibody
ABW	Actual body weight
AE(s)	adverse event(s)
ALT	alanine aminotransferase (also SGPT)
ANC	Absolute Neutrophil Count
aPTT	activated partial thromboplastin time
ARV	antiretroviral
AST	aspartate aminotransferase (also SGOT)
AV	atrioventricular
BMD	Bone Mineral Density
BMI	Body Mass Index
BW	body weight
CD4+	cluster of differentiation 4+
CFR	Code of Federal Regulations
CHF	congestive heart failure
CI	confidence interval
CLCr	creatinine clearance rate
CLDQ-HCV	Chronic Liver Disease Questionnaire
CM	concomitant medication
cm ²	square centimeter
C _{max}	the maximum observed serum/plasma/peripheral blood mononuclear (PBMC) concentration of drug
CRO	contract (or clinical) research organization
CSR	Clinical study report
CT	Computerized Tomography
DAA	direct-acting antiviral
dL	deciliter
DNA	deoxyribonucleic acid
DSPH	Gilead Drug Safety and Public Health
ECG	electrocardiogram
eCRF	electronic case report form
EDC	electronic data capture
eg	example given
ER	Emergency room
ESRD	End Stage Renal Disease
ET	Early Termination
EU	European Union

EudraCT	European Union Drug Regulating Authorities Clinical Trials
FACIT-F	Fatigue Index
FAS	full analysis set
FCF	yellow # 6 / sunset yellow FCF aluminum lake
FD&C	Federal Food, Drug and Cosmetic
FDA	(United States) Food and Drug Administration
FDC	Fixed-dose combination
FEV1	forced expiratory volume in 1 second
FSH	Follicle stimulating hormone
g	grams
GCP	Good Clinical Practice
GGT	gamma glutamyl transferase
GI	giga

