8.5. Efficacy Analysis

8.5.1. Primary Analysis

The primary endpoint is SVR12 in the Full Analysis Set (FAS) population.

In the primary efficacy analysis, the point estimate and the 2-sided 95% exact confidence interval of SVR12 rate will be provided for the overall FAS population and by treatment group.

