8.5.2. Secondary Analyses

The proportion of subjects with HCV RNA below the LLOQ over time (including SVR endpoints) will be presented by treatment group in tabular and graphical form.

Descriptive summaries and listings will be provided for additional efficacy evaluations of the proportion of subjects who experience virologic failure, HCV RNA actual values and change from baseline.

CCI

Details on efficacy analyses will be described in the statistical analysis plan.

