8.9. Sample Size

With a sample size of 100 subjects, a 2-sided 95% exact confidence interval will extend at the most 20% in length.

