### 6.2.2. Analysis Methods for Secondary Efficacy Endpoints

For analyses of HCV RNA  $< \text{LLOQ}$  by visit while on treatment and during the posttreatment (SVR) follow-up period, subjects will be assigned a value at each visit based on the analysis visit windows specified in Section 3.6.2. Missing values will be imputed based on the categorical imputation rules described in Section 3.4.1. The 2-sided 95% exact CI based on Clopper-Pearson method will be provided for the percentage of subjects with HCV RNA  $< \text{LLOQ}$  at each visit within each genotype. The overall category for “HCV RNA  $< \text{LLOQ}$ ” will be split into the following 2 subcategories: “ $< \text{LLOQ TND}$ ” for subjects with target not detected and “ $< \text{LLOQ detected}$ ” for subjects with  $< \text{LLOQ}$  in tabular displays.

Graphs for the percentage of subjects with HCV RNA  $< \text{LLOQ}$  over time during treatment will be displayed by genotype.

Summary statistics will be presented for absolute values and change from baseline in HCV RNA ( $\log_{10}$  IU/mL), by genotype and by visit through EOT. Imputation rules described in Section 3.4.1 will be used to assign HCV RNA values for missing values at a visit that are bracketed by “ $< \text{LLOQ TND}$ ” and/or “ $< \text{LLOQ detected}$ ”. Otherwise, a missing = excluded analysis will be performed. Plots of the mean  $\pm$  SD and median (Q1, Q3) of absolute values and changes from baseline in HCV RNA through EOT will be presented.

For the SVR12 endpoint analysis, a summary table of the number and percentage of subjects with SVR12, virologic failure, and Other by genotype will be created. All subjects who achieve SVR12 will be categorized as SVR12. Virologic failure will be descriptively summarized as

“on-treatment virologic failure” and relapse (which will be broken down by study drug completed yes/no). Subjects who do not achieve SVR12 and do not meet criteria for virologic failure will be categorized as “Other.” The denominator for relapse will be the number of subjects who had HCV RNA < LLOQ on their last observed on-treatment HCV RNA measurement; otherwise, the denominator will be the number of subjects in the FAS.

A concordance table between SVR12 and SVR24 will be provided for each genotype. Subjects with both observed SVR12 and observed SVR24 data will be included for this analysis.

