#### **6.4. Changes From Protocol-Specified Efficacy Analyses**

There are no planned changes from protocol-specified efficacy analyses.

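### SAP 6.1.2 specifies the primary SVR12 analysis by genotype and omits the overall and by-treatment-group estimates that the protocol makes primary, while SAP 6.4 reports no change

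*SAP*

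**What the plan says.** Protocol 8.5.1 states what is primary for efficacy: "the point estimate and the 2-sided 95% exact confidence interval of SVR12 rate will be provided for the overall FAS population and by treatment group". The synopsis agrees: "exact confidence interval of SVR12 rate will be provided for each treatment group and overall". For the secondary analyses, protocol 8.5.2 says that the proportion below LLOQ over time, SVR endpoints included, "will be presented by treatment group in tabular and graphical form".

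SAP 6.1.2 reads "The SVR12 rate in each of genotype will be calculated along with 2-sided 95% exact CI", using the Clopper-Pearson method. It mentions no other unit of analysis. SAP 6.2.2 gives the by-visit intervals within each genotype and says that the graphs of the percentage below LLOQ "over time during treatment will be displayed by genotype". SAP 6.4 closes the efficacy section: "There are no planned changes from protocol-specified efficacy analyses".

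Two general sections of the SAP point the other way. Section 3.1.2 groups the FAS by genotype and treatment group. Section 3.2 sets the same grouping for FAS analyses and lists default columns: GT1a, GT1b, GT1 Other, GT1 total, GT4, GT5, GT6, Indeterminate and Total.

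The only sample-size statement, the same in both documents, is: "With a sample size of 100 subjects, a 2-sided 95% exact confidence interval will extend at the most 20% in length".

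**The concern.** The primary objective in both documents is SVR12 after 8, 12 or 24 weeks of treatment. The estimates that address it are those by treatment group, and the estimate that the sample size supports is the overall one. The section that should specify both specifies neither, and puts in their place a breakdown that the protocol does not call primary. Because 6.4 reports no change, a reader of the study report would not be told that the primary table differs from the protocol. A programmer who follows 6.1.2 to the letter could deliver genotype columns, perhaps with a total, and no per-regimen estimate.

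**Working it through.** **1. The plan's own figure.** Inputs: n = 100 and a 2-sided 95% exact interval (protocol 8.9, SAP 1.3). For x responders the Clopper-Pearson limits are

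- lower = the 0.025 quantile of Beta(x, n − x + 1)
- upper = the 0.975 quantile of Beta(x + 1, n − x)

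The width is greatest at x = 50: 39.83% to 60.17%, a width of 20.34%. This reproduces the stated 20% after rounding. The statement is a function of n = 100, so it describes the overall estimate only. Neither document plans a size per treatment group or per genotype. With assumed sizes of 25, 33 and 50, the greatest width is 40.9%, 35.7% and 28.9%.

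**2. Genotype against regimen.** From the group definitions in protocol 3.3 and SAP 1.2:

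| Genotype | Group 1 (8 weeks) | Group 2 (12 weeks) | Group 3 (24 weeks) |
|---|---|---|---|
| 1 | naïve, no cirrhosis | experienced, no cirrhosis | compensated cirrhosis |
| 4, 5, 6 | none | no cirrhosis, naïve or experienced | compensated cirrhosis |

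Every genotype row mixes at least two durations, and the genotype 1 row mixes all three. No row or sum of rows isolates a group.

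**3. What a genotype-only table hides.** Assume, for illustration, 100 genotype 1 subjects split 45/30/25 across Groups 1, 2 and 3, with 95 responders in total. The genotype row is 95.0% (88.7% to 98.4%) in each of these cases:

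- A: 45/45, 30/30, 20/25. Group 3 is 80.0% (59.3% to 93.2%).
- B: 40/45, 30/30, 25/25. Group 1 is 88.9% (75.9% to 96.3%).
- C: 45/45, 25/30, 25/25. Group 2 is 83.3% (65.3% to 94.4%).

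The three cases differ on which duration falls short, and the table is the same for all of them.

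**4. Does another SAP section supply the missing estimates?** Section 3.2 states the two-way grouping, but its listed columns are genotypes and Total; there is no Group 1, 2 or 3 column. The list is a default that a specific section may override, and 6.1.2 can be read as doing so. Treatment group is absent from the subgroup factors in 3.3 and from the readable efficacy text of Section 6. The SAP does name it where it is wanted: disposition (4.1), adherence (4.2.2), demographics (5.1) and medical history (5.3).

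**The case against.** The strongest reply is that the SAP must be read as a whole. Sections 3.1.2 and 3.2 govern FAS analyses, SVR12 is defined in the FAS, the grouping there includes treatment group, and Total is the overall rate. This stands in part. A reader might infer from 6.1.2 that the protocol's analysis has been replaced and that the primary question will go unanswered. The documents do not support that, because the protocol's estimates may still be produced under 3.2. They are implied rather than specified, however, and a primary analysis should not depend on that inference.

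Other points in the plan's favour:

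- Cirrhosis is a listed subgroup with exact intervals. If it is shown in the Total column it gives the 24-week rate, since Group 3 is the cirrhotic group. No single planned subgroup isolates Group 1 or Group 2.
- A reader might conclude that every genotype layout in 6.1.3 and 6.2.2 departs from the protocol. It does not. Protocol 8.5.2 requires treatment-group display only for the proportion below LLOQ over time. It names no grouping for virologic failure or for HCV RNA values and change, and its readable text prescribes no subgroup layout.
- Wide intervals in small genotype cells do not measure this defect. If a cell held 5 subjects (an assumption), 5/5 would give 47.8% to 100%, but a treatment group could be small too.
- The study is open-label and descriptive, with no hypothesis test at stake, and all the variables needed are collected. The text may be carried over from another plan (6.2.1 refers to SOF/VEL, which is not the study drug). That is an inference, and it does not alter what 6.1.2 says.

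**Conclusion.** Wrong as written. SAP 6.1.2 specifies a primary analysis that does not match protocol 8.5.1 or the synopsis, and 6.4 is incorrect in saying that nothing changed. The general rule in 3.1.2 and 3.2 makes it possible, not certain, that the right estimates will appear.

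The size of the problem is a matter of which quantity is estimated. A genotype-only table leaves SVR12 undetermined for all three durations; in the example one and the same table is compatible with 80.0%, 83.3% or 88.9% in one group and 100% in the other two. That example rests on an assumed all-genotype-1 sample and an assumed 45/30/25 split. The overlap of genotypes across groups comes from the group definitions and needs no assumption. The sample size and its 20% statement are unaffected, provided that the statement is read as covering the overall estimate only.

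**What to change.** - **SAP 6.1.2:** give the SVR12 rate and 2-sided 95% Clopper-Pearson interval for the overall FAS and for each of Groups 1, 2 and 3. Describe the genotype estimates as supportive.
- **SAP 6.2.2:** present the proportion with HCV RNA below LLOQ over time, including SVR4 and SVR24, by treatment group in both tables and graphs, as protocol 8.5.2 requires.
- **SAP 6.4:** list any departure from the protocol that remains.

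The genotype layouts of the other 6.2.2 summaries and of the 6.1.3 subgroups may stay, and genotype is already a subgroup factor in 3.3. The cost is SAP wording and table shells. No new data are needed and the sample size does not change.

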#### 6.1.3. Subgroup Analysis of the Primary Efficacy Endpoint

The point estimates and 95% exact CIs of the SVR12 rates will be displayed by genotype for subgroups outlined in Section [3.3](#).

SVR12 rates will be summarized by categories of early viral response to explore possible early on-treatment predictors of SVR12. The relationship between SVR12 and study drug interruption may also be explored. A forest plot will graphically present estimates and 95% CIs in SVR12 rates for each of the subgroups.

## 6.2. Secondary Efficacy Endpoints

### 6.2.1. Definition of Secondary Efficacy Endpoints

Secondary efficacy endpoints include the following:

- The percentage of subjects with HCV RNA < LLOQ at 4 and 24 weeks after discontinuation of treatment (SVR4 and SVR24)
- The percentage of subjects with HCV RNA < LLOQ while on treatment by study visit
- HCV RNA ( $\log_{10}$  IU/mL) and change from baseline in HCV RNA ( $\log_{10}$  IU/mL) through end of treatment (EOT)
- The percentage of subjects with virologic failure as the following:
  - On-treatment virologic failure
    - HCV RNA  $\geq$  LLOQ after having previously had HCV RNA < LLOQ, while on treatment, confirmed with 2 consecutive values (note, second confirmation value can

be posttreatment), or last available on-treatment measurement with no subsequent follow up values (ie, breakthrough)

- $> 1 \log_{10}\text{IU/mL}$  increase in HCV RNA from nadir while on treatment, confirmed with 2 consecutive values (note, second confirmation value can be posttreatment), or last available on-treatment measurement with no subsequent follow up values (ie, rebound)
- HCV RNA persistently  $\geq \text{LLOQ}$  through 8 weeks of treatment (ie, nonresponse)

— Relapse

- HCV RNA  $\geq \text{LLOQ}$  during the posttreatment period having achieved HCV RNA  $< \text{LLOQ}$  at end of treatment, confirmed with 2 consecutive values or last available posttreatment measurement

- The steady-state pharmacokinetics of LDV and SOF and its metabolites in subjects who are on dialysis for End Stage Renal Disease (ESRD)
- Characterization of HCV drug resistance substitutions at baseline, during, and after therapy with SOF/VEL.

### 6.2.2. Analysis Methods for Secondary Efficacy Endpoints

For analyses of HCV RNA  $< \text{LLOQ}$  by visit while on treatment and during the posttreatment (SVR) follow-up period, subjects will be assigned a value at each visit based on the analysis visit windows specified in Section 3.6.2. Missing values will be imputed based on the categorical imputation rules described in Section 3.4.1. The 2-sided 95% exact CI based on Clopper-Pearson method will be provided for the percentage of subjects with HCV RNA  $< \text{LLOQ}$  at each visit within each genotype. The overall category for “HCV RNA  $< \text{LLOQ}$ ” will be split into the following 2 subcategories: “ $< \text{LLOQ TND}$ ” for subjects with target not detected and “ $< \text{LLOQ detected}$ ” for subjects with  $< \text{LLOQ}$  in tabular displays.

Graphs for the percentage of subjects with HCV RNA  $< \text{LLOQ}$  over time during treatment will be displayed by genotype.

Summary statistics will be presented for absolute values and change from baseline in HCV RNA ( $\log_{10}$  IU/mL), by genotype and by visit through EOT. Imputation rules described in Section 3.4.1 will be used to assign HCV RNA values for missing values at a visit that are bracketed by “ $< \text{LLOQ TND}$ ” and/or “ $< \text{LLOQ detected}$ ”. Otherwise, a missing = excluded analysis will be performed. Plots of the mean  $\pm$  SD and median (Q1, Q3) of absolute values and changes from baseline in HCV RNA through EOT will be presented.

For the SVR12 endpoint analysis, a summary table of the number and percentage of subjects with SVR12, virologic failure, and Other by genotype will be created. All subjects who achieve SVR12 will be categorized as SVR12. Virologic failure will be descriptively summarized as

“on-treatment virologic failure” and relapse (which will be broken down by study drug completed yes/no). Subjects who do not achieve SVR12 and do not meet criteria for virologic failure will be categorized as “Other.” The denominator for relapse will be the number of subjects who had HCV RNA < LLOQ on their last observed on-treatment HCV RNA measurement; otherwise, the denominator will be the number of subjects in the FAS.

A concordance table between SVR12 and SVR24 will be provided for each genotype. Subjects with both observed SVR12 and observed SVR24 data will be included for this analysis.

Drug resistant substitutions will be analyzed and reported based on change from baseline sequence and/or change from HCV genotype reference strain as part of the Virology Study Report.

### 6.3. Exploratory Efficacy Endpoints

CCI

CCI

#### **6.4. Changes From Protocol-Specified Efficacy Analyses**

There are no planned changes from protocol-specified efficacy analyses.

## 7. SAFETY ANALYSES

### 7.1. Adverse Events and Deaths

The primary safety endpoint is any AE that led to permanent discontinuation of study drug.

#### 7.1.1. Adverse Event Dictionary

Clinical and laboratory adverse events (AEs) will be coded using the current version of MedDRA. System organ class (SOC), high-level group term (HLGT), high-level term (HLT), preferred term (PT), and lower-level term (LLT) will be provided in the AE dataset.

#### 7.1.2. Adverse Event Severity

Adverse events are graded by the investigator as Grade 1, 2, 3, or 4 according to toxicity criteria specified in the protocol. The severity grade of events for which the investigator did not record severity will be categorized as “missing” for tabular summaries and data listings, and the most severe will be considered (for sorting purpose only) in data presentation.

#### 7.1.3. Relationship of Adverse Events to Study Drug

Related AEs are those for which the investigator selected “Related” on the AE case report form (CRF) to the question of “Related to Study Treatment.” Events for which the investigator did not record the relationship to study drug will be considered to be related to study drug for summary purposes. However, by-subject data listings will show the relationship as missing from that captured on the CRF.

